5.2.2 Screen Failures/Dropouts

A subject who discontinues study participation prematurely for any reason is defined as a “dropout” if the subject has already been randomized; assigned to treatment/run-in/wash-out; or had at least one dose of study drug administered.

A subject who, for any reason (e.g. failure to satisfy the selection criteria) terminates the study before the time point used for the definition of “dropout” (see above) is regarded a “screening failure”.

5.2.3 Replacement

Subjects who withdraw from the study prior to undergoing the first biopsy will be replaced.

5.3.1 Personnel

At each site, personnel dedicated to this protocol will be:

- A study PI
- A research coordinator
- A data manager

In addition, at Lombardi-Georgetown, there will be a dedicated “multi-institutional” research coordinator who will play the primary role in coordinating the trial between Lombardi-Georgetown and additional sites. This coordinator will be the main point of contact for [name] and the other site PIs for any study related concerns, and to screen each patient being considered for enrollment (Including “remote” screening for the patients being screened at other sites). This coordinator will also be the point of contact for the data managers for data entry questions. Finally, this coordinator will play a major role in regulatory coordination of the study, specifically by: 1) Reviewing and confirming all study-related adverse events; 2) Submitting all SAE reports to the Georgetown IRB (The research coordinators at the other sites will prepare SAE reports for patients treated at their respective sites, but the “multi-institutional” coordinator will submit the final report); 3) Gathering and preparing all primary source data for review/audit by Theradex, Inc.

5.3.2 Patient Enrollment

Enrollment at the sites will be competitive. If a patient is being screened for enrollment, the local research coordinator must send an email within 24 - 48 hours containing the subject number, to the PI, and to the multi-institutional coordinator. If a patient is successfully screened, the local research coordinator must send all supporting documentation to the multi-institutional research coordinator (by email [[contact]]). Patients should not start therapy until both PI and the multi-institutional coordinator have reviewed the patient’s records and confirmed that the patient is indeed eligible for enrollment.

5.3.3 Data Collection and Management

Patient data will be entered into the on-line accessible database. This database is housed at Lombardi-Georgetown, but is accessible anywhere there is internet access. The data manager and research coordinator at each site will attend an on-line training session so that they may learn how to enroll data into the database. All screening data should be entered prior to starting therapy, and all ongoing patient data should be entered within one week of each patient visit.

5.3.4 Conference Calls

A monthly conference call will be held between Lombardi-Georgetown and the other sites to review patient enrollment, toxicity, and response assessment.

6. Treatment[s]

6.1 Blinding

Given the nature of this trial, patient or investigator blinding will not be necessary.

6.2 Study Treatment

As Regorafenib is commercially available, patients will be provided a prescription and will fill it from retail or specialty pharmacies.

Regorafenib is administered as monotherapy during the study; 120 mg qd will be administered for 3 weeks on /1 week off. One cycle is 28 days.

Three 40-mg regorafenib tables should be taken in the morning with approximately 8 fluid ounces (240 mL) of water after a low-fat (<30% fat) breakfast. Some examples of low fat breakfasts are:

- Two slices of white toast with 1 tablespoon of low-fat margarine and 1 tablespoon of jelly and 8 ounces (240 mL) of skim milk (approximately 319 calories and 8.2 g of fat).
- One cup of cereal (i.e. Special K), 8 ounces (240 mL) of skim milk, one piece of toast with jam (no butter or marmalade), apple juice, and one cup of coffee or tea (2 g fat, 17 g protein, 93 g of carbohydrate, 520 calories).


a. NCI-CTCAE = National Cancer Institute - Common Terminology Criteria for Adverse Events, version 4.0
 
b. Excludes alopecia, non-refractory nausea/vomiting, non-refractory hypersensitivity and nonclinical and asymptomatic laboratory abnormalities.
 
c. If no recovery after a 4 week delay*, treatment should be permanently discontinued unless subject is deriving clinical benefit.
			

The table above outlines dose adjustments for hematologic and non-hematologic toxicities related to regorafenib except HFSR and hypertension.

In addition to these recommended dose modifications, subjects who develop diarrhea, mucositis, anorexia or other events predisposing to fluid loss or inadequate fluid intake should be carefully monitored and rehydrated as clinically necessary. This is in order to minimize the risk of postural hypotension and renal failure.

Table 6-2: Grading for Hand-Foot-Skin-Reaction			
	Grade 1	Grade 2	Grade 3
NCI-CTCAE v4.0 Palmar-plantar erythrodysesthesia syndrome	Minimal skin changes or dermatitis (e.g., erythema, edema, or hyperkeratosis) without pain	Skin changes (e.g., peeling, blisters, bleeding, edema, or hyperkeratosis) with pain	Severe skin changes (e.g., peeling, blisters, bleeding, edema, or hyperkeratosis) with pain
Further description / examples of skin changes	Numbness, dysesthesia / paresthesia tingling, painless swelling, or erythema of the hands and/or feet	Painful erythema and swelling of the hands and/or feet	Moist desquamation, ulceration, blistering, or severe pain of the hands and/or feet
Effect on activities	Does not disrupt normal activities	Limiting instrumental activities of daily life (e.g., preparing meals, shopping for groceries or clothes, using the telephone, managing money)	Limiting self-care activities of daily life (e.g., bathing, dressing and undressing, feeding self, using the toilet, taking medications) and not bedridden
a. Palmer-planter erythrodysesthesia syndrome is a disorder characterized by redness, marked discomfort, swelling, and tingling in the palms of hands or the soles of the feet.			

Table 6.3 Recommended dose modification for hand-foot-skin reaction^a

Grade of event (NCI-CTCAE v4.0)	Occurrence	Suggested Dose Modification
Grade 1	Any	Maintain dose level and immediately institute supportive measures for symptomatic relief
Grade 2	1 st occurrence	Consider decreasing dose by one dose level and immediately institute supportive measures. If no improvement, interrupt therapy for a minimum of 7 days, until toxicity resolves to Grade 0-1 ^{b, c}
	No improvement within 7 days or 2 nd occurrence	Interrupt therapy until toxicity resolves to Grade 0-1. ^c When resuming treatment, treat at reduced dose level ^b
	3 rd occurrence	Interrupt therapy until toxicity resolves to Grade 0-1. ^c When resuming treatment, decrease dose by one dose level. ^{b, d}
	4 th occurrence	Discontinue therapy
Grade 3	1 st occurrence	Institute supportive measures immediately. Interrupt therapy for a minimum of 7 days until toxicity resolves to Grade 0-1. ^c When resuming treatment, decrease dose by one dose level. ^{b, d}
	2 nd occurrence	Institute supportive measures immediately. Interrupt therapy for a minimum of 7 days until toxicity resolves to Grade 0-1. ^c When resuming treatment, decrease dose by one additional dose level ^{b, d}
	3 rd occurrence	Discontinue treatment permanently.

- a. More conservative management is allowed if judged medically appropriate by the investigator.
- b. If toxicity returns to Grade 0-1 after dose reduction, dose re-escalation is permitted at the discretion of the investigator if subject has completed one cycle at reduced dose without recurrence of event.
- c. If there is no recovery after a 4-week delay, treatment with regorafenib will be discontinued permanently.
- d. Subjects requiring > 2 dose reductions should go off protocol therapy.
- e. The maximum daily dose is 120 mg.

(For studies with combination therapy, consider including the following statement “The other study treatment may be continued”).

At first occurrence of HFSR, independent of grade, prompt institution of supportive measures such as topical emollients, low potency steroids, or urea-containing creams should be administered.

Recommended prevention/management strategies for skin toxicities consistent with HFSR are summarized below:

Control of calluses

Before initiating treatment with regorafenib:

- Check condition of hands and feet.
- Suggest a manicure/pedicure, when indicated.
- Recommend pumice stone use for callus or 'rough spot' removal.

During regorafenib treatment:

- Avoid pressure points.
- Avoid items that rub, pinch or create friction.

Use of creams

- Non-urea based creams may be applied liberally.
- Keratolytic creams (e.g. urea-based creams, salicylic acid 6%) may be used sparingly and only to affected (hyperkeratotic) areas.
- Alpha hydroxyl acids (AHA) based creams may be applied liberally 2 times a day. Approximately 5% to 8% provides gentle chemical exfoliation.
- Topical analgesics (e.g. lidocaine 2%) are to be considered for pain control.
- Topical corticosteroids like clobetasol 0.05% should be considered for subjects with Grade 2 or 3 HFSR. Avoid systemic steroids.

Tender areas should be protected as follows:

- Use socks/gloves to cover moisturizing creams
- Wear well-padded footwear
- Use insole cushions or inserts (e.g. silicon, gel)
- Foot soaks with tepid water and Epsom salts

Hypertension

Hypertension is a known AE associated with regorafenib treatment. Subject will have their blood pressure measured at least weekly at the study site during the first 6 weeks of treatment. If additional blood pressure measurements are done outside the study site, and the blood pressure is > 140 mm Hg systolic or > 90 mm Hg diastolic (NCI CTCAE v4.0), then the subject must contact study personnel. The management of hypertension, including the choice of antihypertensive medication, will be performed according to local standards and to the usual practice of the investigator. Every effort should be made to control blood pressure by medical means other than study drug dose modification. If necessary, Table 6-4 outlines suggested dose reductions.

Grade (CTCAE v4.0)	Antihypertensive Therapy	Regorafenib Dosing

1
 
Prehypertension (systolic BP 120 - 139 mmHg or diastolic BP 80 - 89 mmHg)
	
None
	
 • Continue regorafenib • Consider increasing blood pressure (BP) monitoring

2
 
Systolic BP 140 - 159 mmHg or diastolic BP 90 - 99 mmHg, OR Symptomatic increase by > 20 mmHg (diastolic) if previously within normal limits
	
 • Treat with the aim to achieve diastolic BP \leq 90 mm Hg: • If BP previously within normal limits, start anti-hypertensive monotherapy • If patient already on anti-hypertensive medication, titrate up the dose. 	
 • Continue regorafenib • If symptomatic, hold regorafenib until symptoms resolve AND diastolic BP \leq 90 mm Hg^a. When regorafenib is restarted, continue at the same dose level.

3
 
Systolic BP \geq 160 mmHg or diastolic BP \geq 100 mmHg OR More than one drug or more intensive therapy than previously used indicated
	
Treat with the aim to achieve diastolic BP \leq 90 mm Hg: Start anti-hypertensive medication
 
AND/OR Increase current anti-hypertensive medication
 
AND/OR Add additional anti-hypertensive medications.
	
 • Hold regorafenib until diastolic BP \leq 90 mm Hg, and if symptomatic, until symptoms resolve.^a • When regorafenib is restarted, continue at the same dose level. • If BP is not controlled with the addition of new or more intensive therapy, reduce by 1 dose level.^b • If Grade 3 hypertension recurs despite dose reduction and antihypertensive therapy, reduce another dose level.^c

4
 
Life-threatening consequences (e.g., malignant hypertension, transient or permanent neurologic deficit, hypertensive crisis)
	
Per institutional guidelines
	
Discontinue therapy

a. Patients requiring a delay of >4 weeks should go off protocol therapy
 
b. If BP remains controlled for at least one cycle, dose re-escalation permitted per investigator's discretion.
 
c. Patients requiring >2 dose reductions should go off protocol therapy.
		

Table 6-4: Management of Treatment-Emergent Hypertension

Liver Function Abnormalities

For patients with observed worsening of serum liver tests considered related to regorafenib (i.e. where no alternative cause is evident, such as post-hepatic cholestasis or disease progression), the dose modification and monitoring advice in Table 6-5 should be followed.

Regorafenib is a UGT1A1 inhibitor. Mild, indirect (unconjugated) hyperbilirubinemia may occur in patients with Gilbert’s syndrome.

Table 6.5: Recommended measures and dose modifications in case of drug-related liver function test abnormalities

Observed elevations of ALT and/or AST	Occurrence	Recommended measures and dose modification
≤ 5 times upper limit of normal (ULN) (maximum Grade 2)	Any occurrence	Continue Regorafenib treatment. Monitor liver function weekly until transaminases return to < 3 times ULN (Grade 1) or baseline.
>5 times ULN to ≤ 20 times ULN (Grade 3)	1 st occurrence	Interrupt Regorafenib treatment. Monitor transaminases weekly until return to < 3 times ULN or baseline. Restart: If the potential benefit outweighs the risk of hepatotoxicity, re-initiate Regorafenib treatment, reduce dose by 40 mg (one tablet), and monitor liver function weekly for at least 4 weeks.
	Re-occurrence	Discontinue treatment with Regorafenib permanently.
>20 times ULN (Grade 4)	Any occurrence	Discontinue treatment with Regorafenib permanently.
>3 times ULN (Grade 2 or higher) with concurrent bilirubin >2 times ULN	Any occurrence	Discontinue treatment with Regorafenib permanently. Monitor liver function weekly until resolution or return to baseline. Exceptions: patients with Gilbert’s syndrome who develop elevated transaminases should be managed as per the above outlined recommendations for the respective observed elevation of ALT and/or AST.

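### In Table 6-4 an asymptomatic Grade 3 hypertension hold ends on diastolic pressure alone, so a patient at 175/85 meets the restart condition while still in the Grade 3 pressure range

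*Combined protocol and SAP*

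**What the plan says.** All of the governing text is in Section 6.2.1, under Hypertension and in Table 6-4.

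- **Entry to Grade 3.** Either pressure is enough: systolic 160 mm Hg or more, or diastolic 100 or more. A third route is treatment-based: "More than one drug or more intensive therapy than previously used indicated".
- **Release from the Grade 3 hold.** "Hold regorafenib until diastolic BP" is at or below 90 mm Hg, and symptoms must also clear if the patient has any. The dose on restart is the same dose level.
- **Treatment aim for Grade 3.** "Treat with the aim to achieve diastolic BP" at or below 90 mm Hg. There is no systolic aim.
- **Backstop.** "If BP is not controlled with the addition of new or more intensive therapy, reduce by 1 dose level". If Grade 3 recurs after that, the dose drops another level.
- **Grade 2 row.** The range is "Systolic BP 140 - 159 mmHg or diastolic BP 90 - 99 mmHg". Asymptomatic patients in it continue regorafenib.
- **Limit on delay.** Footnote a: "Patients requiring a delay of >4 weeks should go off protocol therapy".
- **Status of the table.** "If necessary, Table 6-4 outlines suggested dose reductions". Management of hypertension "will be performed according to local standards and to the usual practice of the investigator". The same paragraph prefers medical control of blood pressure to changing the study drug dose. It also tells subjects to contact study personnel if a reading taken outside the site exceeds 140 systolic or 90 diastolic.

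**The concern.** A hold should end when the value that caused it has improved. Here systolic pressure can start the hold but plays no part in ending it. A patient held for isolated systolic elevation has nothing to recover from under the release rule, because diastolic pressure was never high. The treatment aim has the same blind spot.

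Hypertension is a known adverse event of regorafenib, as Section 6.2.1 says. What is at stake is re-exposure to the drug while systolic pressure is still at the level for which the table requires interruption.

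**Working it through.** There is no plan figure to reproduce. The check is whether the written entry and release rules can both be true at one reading.

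**Rules, for an asymptomatic patient, pressure criteria only**

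- Grade 3 pressure range: SBP ≥ 160 or DBP ≥ 100 (Table 6-4, Grade 3 row).
- Release as written: DBP ≤ 90 (same row).
- Both hold together when SBP ≥ 160 and DBP ≤ 90. That region is the whole of the gap.

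**Illustrative readings.** These were chosen to sit on either side of the boundaries, so they say nothing about frequency.

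| Reading | Grade 3 pressure? | As written | If SBP < 160 also required | If SBP < 140 also required |
|---|---|---|---|---|
| 175/85 | yes | released | held | held |
| 160/90 | yes | released | held | held |
| 175/91 | yes | held | held | held |
| 165/105 | yes | held | held | held |
| 159/90 | no | released | released | held |

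**Does any other rule supply a systolic restart value?**

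- Table 6-1 delays treatment for Grade 3 events until Grade 2 or lower. It would close the gap, but its title and the text beneath it exclude hypertension.
- Hand-foot skin reaction (Table 6.3) resumes at Grade 0-1, and transaminases (Table 6.5) at below 3 times the upper limit of normal or baseline. Each releases on the measure that caused the interruption. Table 6-4 does not.
- The backstop on uncontrolled pressure sets the dose level and does not prolong the hold. Table 6-4 does not define control. Borrowing the figures in Section 5.1.2 (above 140 systolic or above 90 diastolic) is an inference, since that is an eligibility criterion. Even so read, a patient at 165/88 after new therapy would drop from 120 to 80 mg but would not stay on hold.

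**Interval to the next scheduled check.** Section 6.5 asks for weekly pressures for six weeks, then every cycle or more often if clinically indicated. The scheduled gap is 7 days in weeks 1 to 6. From cycle 3 it is Day 1 to Day 1: day 57 to day 85, or 28 days, of which 21 are dosing days. The 28-day figure is a worst case. It assumes restart on Day 1 of a cycle, no extra check and no outside reading.

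**Size.** Section 1.2.2 reports Grade 3 or higher hypertension in 7% of regorafenib patients in the colorectal trial at 160 mg: 0.07 × 40 = 2.8, about 3 patients. The gastrointestinal stromal tumor trial is given as 48.5%, also at 160 mg: 0.485 × 40 = 19.4. The first is the matching disease. Neither is at this trial's 120 mg starting dose, and neither is split by systolic and diastolic pressure.

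**The case against.** The strongest case against is that the table is advisory and the rest of the row protects the patient. Local standards govern, and the table's dose changes are only suggestions. The row calls for starting, raising or adding antihypertensives whichever pressure triggered Grade 3. Pressure that stays uncontrolled brings a dose reduction. Outside readings above 140 systolic must be reported. A reader might infer that the protocol orders full-dose restart in patients with severe systolic hypertension. The documents do not support that: the row sets a condition for ending the hold, and an investigator may wait longer.

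All of this stands as mitigation, but none of it supplies a systolic restart value. Section 12.1 demands strict adherence to the protocol's specifications. The hand-foot table has a footnote allowing more conservative management; Table 6-4 has none.

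A second objection concerns the replacement value. It is tempting to say that 160 follows from the table because asymptomatic patients at 140-159 continue drug. That argument fails: asymptomatic patients at diastolic 90-99 also continue, yet release from a Grade 3 hold requires 90 or lower. A 160 limit would release 159/88 while 120/95 stays held. The closer parallel may be 140, which the protocol pairs with diastolic 90 in Section 5.1.2 and in the outside-reading rule. So 160 can be defended only as a floor.

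Two extensions also fail. The Grade 2 row is diastolic-only too, but its hold is triggered by symptoms, and asymptomatic patients at systolic 140-159 continue anyway. The treatment-based route into Grade 3 can persist at normal pressure, so it is not a sensible restart test.

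**Conclusion.** The point holds as a gap in a stated rule. For an asymptomatic patient, any reading with systolic 160 or more and diastolic 90 or less satisfies the restart condition while still in the Grade 3 pressure range, and nothing else in the protocol provides a systolic threshold for restart.

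The number affected is unknown and probably small. At the colorectal rate it is some fraction of about 3 patients in 40, on the assumption that a 160 mg rate carries over to 120 mg. Many investigators would hold longer on their own judgment. This is a minor safety correction, and sample size and analysis are untouched.

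**What to change.** Change the Grade 3 dosing instruction to: *Hold regorafenib until systolic BP is below the Grade 3 range (<160 mm Hg) AND diastolic BP is ≤90 mm Hg and, if the patient is symptomatic, symptoms have resolved.* Add a systolic goal to the Grade 3 antihypertensive aim, with its value set by the clinical team.

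The 160 limit is the minimum needed so that nobody restarts while still in the Grade 3 pressure range. The clinical team may prefer a lower limit such as 140, which would also keep patients at systolic 140-159 with diastolic 90 or less on hold.

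The cost is an amendment to one table row, and both pressures are already measured. With the 160 limit, holds can lengthen only for patients with systolic 160 or more and diastolic 90 or less. Those patients carry a small added risk of passing the 4-week limit and leaving protocol therapy. That should be weighed against the protocol's stated preference for controlling pressure by medical means, and it weighs more heavily if a lower limit is chosen.

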6.2.2 Prevention/management strategies for diarrhea

Diarrhea can be a common side effect of regorafenib . The preventive/management strategies for diarrhea should be consistent with local standards (e.g., anti-diarrheals and optimized hydration status).

Anti-diarrhea medications may be introduced if symptoms occur. Previous trials have shown that the diarrhea could be managed with loperamide. The recommended dose of loperamide is 4 mg at first onset, followed by 2 mg every 2 to 4 hours until diarrhea-free for 12 hours.

6.3 Drug logistics and accountability

Regorafenib is an FDA approved agent for metastatic colorectal cancer. It will be prescribed by the investigators or their staff. Patient will obtain it from their retail or specialty pharmacies.

6.4 Treatment compliance

An adequate record of receipt, distribution, and return of all study drugs must be kept in the form of a Drug Accountability Form.

Subject compliance with the treatment and protocol includes willingness to comply with all aspects of the protocol, and to have blood collected for all safety evaluations. At the discretion of the principal investigator, a subject may be discontinued from the trial for non-compliance with follow-up visits or study drug.

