5.2 Withdrawal of subjects from study

5.2.1 Withdrawal

Subjects **must be withdrawn from the trial** (treatment and procedures) for the following reasons:

- Subject withdraws consent from study treatment and study procedures. A subject must be removed from the trial at his/her own request or at the request of his/her legally acceptable representative. At any time during the trial and without giving reasons, a subject may decline to participate further. The subject will not suffer any disadvantage as a result.
- Pregnancy. Pregnancy will be reported as an SAE. (Note: subjects who have been withdrawn from treatment with study drug because of pregnancy should not undergo CT scans [with contrast]/MRI or bone scans while pregnant.)
- If, in the investigator's opinion, continuation of the trial would be harmful to the subject's well-being.
- Subject is lost to follow-up.
- Death.

Subjects **may be** withdrawn from the study for the following reasons:

- The subject is non-compliant with study drug, trial procedures, or both; including the use of anti-cancer therapy not prescribed by the study protocol.

- Severe allergic reaction to regorafenib (such as exfoliative erythroderma or Grade 3 or 4 hypersensitivity reaction).
- The development of a second cancer.
- Development of an intercurrent illness or situation which would, in the judgment of the investigator, significantly affect assessments of clinical status and trial endpoints.
- Deterioration of ECOG performance status to 4.
- Use of illicit drugs or other substances that may, in the opinion of the investigator, have a reasonable chance of contributing to toxicity or otherwise skewing trial result.

Any subject removed from the trial will remain under medical supervision until discharge or transfer is medically acceptable.

In all cases, the reason for withdrawal must be recorded in the CRF and in the subject's medical records.

Details for the premature termination of the study as a whole (or components thereof [e.g. centers, treatment arms, dose steps]) are provided in Section 11 (Premature termination of the study).

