6.5 Prior and concomitant therapy

All medication that is considered necessary for the subject's welfare, and which is not expected to interfere with the evaluation of the study treatment, may be given at the discretion of the investigator. All medications (including contrast media) taken within 2 weeks prior to the start of the study and during the study must be recorded in the subject's source documentation and in the CRF (including start/stop dates, dose frequency, route of administration, and indication). Specific caution should be taken when considering or administering a concomitant medication that is metabolized by the cytochrome enzymes CYP2C8, CYP2B6 and CYP2C9. Such concomitant medication should be avoided, if possible.

Co-administration of a strong CYP3A4 inducer (rifampin) with a single 160 mg dose of Stivarga decreased the mean exposure of regorafenib, increased the mean exposure of the active metabolite M-5, and resulted in no change in the mean exposure of the active metabolite M-2. Avoid concomitant use of Stivarga with strong CYP3A4 inducers (e.g. rifampin, phenytoin, carbamazepine, phenobarbital, and St. John's Wort)

Co administration of a strong CYP3A4 inhibitor (ketoconazole) with a single 160 mg dose of Stivarga increased the mean exposure of regorafenib and decreased the mean exposure of the active metabolites M-2 and M-5. Avoid concomitant use of Stivarga with strong inhibitors of CYP3A4 activity (e.g., clarithromycin, grapefruit juice, itraconazole, ketoconazole, nefazadone, posaconazole, telithromycin, and voriconazole).

Permitted concomitant therapy includes:

- Standard therapies for concurrent medical conditions.
- Supportive care for any underlying illness.
- Palliative radiation therapy is allowed if the target lesion(s) are not included within the radiation field and no more than 10% of the bone marrow is irradiated.
- Granulocyte colony-stimulating factor (G-CSF) and other hematopoietic growth factors may be used in the management of acute toxicity, such as febrile neutropenia, when clinically indicated or at the investigator's discretion. However, they may not be substituted for a required dose reduction. Subjects are permitted to take chronic erythropoietin.
- Treatment with nonconventional therapies (such as acupuncture), and vitamin/mineral supplements are permitted provided that they do not interfere with the study endpoints, in the opinion of the investigator.
- Bisphosphonates

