7.2 Study Procedures (details are provided in the events table (Page 42))

7.2.1 Subject assessments

Physical examinations (including neurological assessment), vital signs (vital sign determinations include heart rate, blood pressure and body temperature - *Vital signs should be taken after a 5-minute resting period. Labs will then be drawn once the vital signs are recorded*), performance status, chemistry, hematology, medication review, and adverse event evaluations will be conducted at screening, on C1D1, C1D14, C2D1, C2D14, D1 of every cycle starting C3, and at the off study visit. Study procedures may be performed 2 days before the scheduled visit date, due to unforeseen or unavoidable circumstances.

Body weight will be recorded during every physical exam. The subject will wear lightweight clothing and no shoes during weighing. Height will be measured at the Screening Visit only; the subject will not wear shoes.

30 days after the patient's "end of treatment" visit; a 30-day follow-up patient survival assessment will be made by [contact] Tumor Imaging and Response Evaluation

Baseline imaging (CT scan) will be carried out for all cohorts within 28 days prior to regorafenib therapy—and then must be performed every 8 weeks (as near to Day 1 as possible; every 2 cycles) following initiation of regorafenib treatment.

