8.4.4.4 Action taken with study treatment

Any action on study treatment to resolve the AE is to be documented using the categories listed below.

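### The Drug Accountability Form in 6.4 does not fit the pharmacy supply in 6.2 and 6.3, and no substitute is specified, so regorafenib intake before samples is not reliably captured or verifiable

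*Combined protocol and SAP*

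**What the plan says.** **Accountability.** Section 6.4 states: "An adequate record of receipt, distribution, and return of all study drugs must be kept in the form of a Drug Accountability Form".

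**Supply.** Section 6.2 says that "patients will be provided a prescription and will fill it from retail or specialty pharmacies". Section 6.3, whose heading covers both logistics and accountability, repeats the route ("Patient will obtain it from their retail or specialty pharmacies") and adds no accountability procedure.

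**Compliance.** Section 6.4 says: "Subject compliance with the treatment and protocol includes willingness to comply with all aspects of the protocol", and adds having blood drawn for safety tests. It gives no measure of tablets taken. Section 5.2.1 lists as a ground for possible withdrawal: "The subject is non-compliant with study drug, trial procedures, or both". Section 6.4 likewise allows discontinuation for non-compliance with study drug. Neither section sets a threshold.

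**Other records that touch on dosing.**
- Section 7.2.1: "medication review, and adverse event evaluations will be conducted at screening, on C1D1, C1D14, C2D1, C2D14, D1 of every cycle starting C3", and at the off-study visit.
- Section 6.5: "All medications (including contrast media) taken within 2 weeks prior to the start of the study and during the study must be recorded", in the source documents and the CRF, with dates and dose frequency.
- Section 8.4.4.4: "Any action on study treatment to resolve the AE is to be documented using the categories listed below". Sections 7.2.1.7 and 8.4 also ask for actions taken as part of each adverse-event record.

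**The concern.** A record of receipt, distribution and return suits a trial in which the site holds the drug. Here it does not, and the plan does not say how a site would obtain the entries. Even a completed form would show tablets supplied and returned, not which doses were taken on which days.

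The on-treatment part of the study depends on those days. Section 4.1 times the second biopsy to come before dose reductions. Section 4.2.2 uses the change from baseline to week 2 to find pathways that regorafenib inhibits or raises, and correlates that change with response. A patient who started late or had stopped by day 14-21 would look like one whose pathways did not respond to the drug. A patient who took too little drug by week 8 could be labelled a non-responder for that reason alone. Samples are banked and analysed late (Sections 4.1 and 4.2.2), and intake not recorded at the time cannot be reliably rebuilt then.

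**Working it through.** **1. The form against the supply route.** Section 6.4 needs three entries.
- Receipt: under 6.2 and 6.3 the patient receives the drug from a pharmacy.
- Distribution: the pharmacy dispenses, not the site.
- Return: no section describes patients bringing back tablets or bottles.

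The form is the only record dedicated to regorafenib supply or compliance, and the plan gives no source for any of its three entries.

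**2. Is there a substitute?** The available text has no diary, tablet count, refill record, drug level or adherence threshold. The calendar row for oral regorafenib marks dosing and defines no check. Section 9 defines no exposure or dose-intensity variable.

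**3. What the partial sources cover.**
- Medication review falls on C1D14 and on Day 1 of each cycle. The biopsy may be as late as day 21, which is 21 − 14 = 7 days after the C1D14 review, and the next scheduled review is C2D1.
- The medication log in 6.5 belongs to the section on prior and concomitant therapy and does not name regorafenib.
- Action on study treatment is recorded when there is an adverse event to resolve.

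None of the three has to show a late first fill or a dose missed without an event.

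**4. Which look-back fits which sample.** Dosing is on days 1-21 of a 28-day cycle.
- Biopsy and draw on day 14: the preceding 7 days are days 7-13. On day 21: days 14-20. Both lie inside the dosing period, so a 7-day look-back is informative.
- Draw on C2D1 (day 29, week 4): the preceding 7 days are days 22-28. On C3D1 (day 57, week 8): days 50-56. Both are the scheduled off week, so a fully adherent patient would show no doses. These draws need the last-dose date and the doses taken in the preceding 21-day dosing period.

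**5. Size, as illustration.** The plan gives no adherence figure, so there is none to reproduce. The power statement in 9.4 concerns a chi-square test of association and is not affected by what follows. Let δ be the mean paired change on drug, σ² the variance of the change, and f the fraction effectively off drug at the second biopsy, with zero mean change off drug. The observed mean change is (1 − f)δ. With σ² unchanged, the pairs needed for the same power rise by 1/(1 − f)².

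| f (assumed) | 1/(1 − f)² | 40 pairs are worth 40 × (1 − f)² |
|---|---|---|
| 10% | 1/0.81 = 1.23 | 32.4 |
| 20% | 1/0.64 = 1.56 | 25.6 |
| 30% | 1/0.49 = 2.04 | 19.6 |

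Forty pairs is the ceiling, because the second biopsy can be waived (Sections 4.1 and 7.2.1.10). Mixing on-drug and off-drug patients adds f(1 − f)δ² to the variance, so with equal spread in both groups the inflation figures are, if anything, low.

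**The case against.** The best reply is that dosing is not left unrecorded. Patients are reviewed for medications and adverse events at C1D14, C2D1, C2D14 and each later Day 1, and blood pressure is taken at the site at least weekly for six weeks (Section 6.2.1). Interruptions for toxicity, probably a common reason for stopping, should appear in the adverse-event records. This stands, and it narrows the gap to start dates, late fills and doses missed without an event.

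It also rules out three stronger readings. A reader might infer that sites cannot complete the form. The documents only fail to say how: pharmacy records or bottles brought to visits are not excluded. A reader might infer that intake is unknown or that self-interruption is invisible. The partial sources contradict that. A reader might infer that every marker result is affected. Section 9.3.1 names as its main goal markers that predict response when measured at baseline. Later intake cannot alter a baseline value and can only blur the response label.

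Two limits apply to the check. CRF pages are not in the documents, and a short stretch of text before 5.3.1 was not available, so an intake field there cannot be excluded.

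**Conclusion.** The point holds in a limited form. Sections 6.2, 6.3 and 6.4 do not fit together, the non-compliance criterion has no measure, and intake before the day 14-21 samples and during each dosing period is not reliably captured or verifiable. The trial can run without the change, but the on-treatment marker results would be harder to interpret.

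The 1.23-, 1.56- and 2.04-fold figures are not estimates for this trial. They assume that 10-30% of patients are off drug, that there is no change off drug and that the variance is unchanged. They apply to the mean paired change only, not to the association between markers and response or to the sample-size basis in 9.4.

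**What to change.** - Reconcile Sections 6.2, 6.3 and 6.4. Replace the form with a patient dosing diary plus a bottle and tablet count, reviewed at C1D14, the day 14-21 biopsy visit and each Day 1.
- Record in the CRF the first-dose date, the actual daily dose, and the doses taken in the 7 days before the day 14-21 biopsy and draw. For Day 1 draws (weeks 4 and 8), record the last-dose date and the doses taken in the preceding 21-day dosing period.
- Repeat the RPPA baseline-to-week-2 analysis in patients documented on drug before the second biopsy. Define any miRNA sensitivity set by doses taken in the preceding dosing period. Report dose intensity to week 8 by response.
- Reconcile the tablet numbers before any count is used. Section 6.2 gives three 40-mg tablets for 120 mg, and the dose-level table in 6.2.1 gives four. A count cannot be turned into a dose until these agree.

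The cost is a one-page diary, a few CRF fields at visits that already take place, and the added sensitivity analyses. Self-report is imperfect and the tablet count corrects it only in part. No dose or clinical rule changes.
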